5.2 EXCLUSION CRITERIA

Subjects who meet the following criteria will be excluded from enrollment:

- Unable or unwilling to provide informed consent or to comply with study procedures
- History of anorectal pathology in the past 6 months (perianal abscess or fistula, fecal impaction, or clinically significant rectocele).
- History of inflammatory bowel disease with active proctosigmoiditis
- History of rectal surgery in past 6 months where the Investigator determines that the use of the study device may be associated with an increased risk of complications.
- History of acute or chronic illness or history of illness or any other reason which in the opinion of the Investigator, could pose a threat or harm to the subject or obscure interpretation of laboratory test results or interpretation of study data such as frequent angina, Class III or IV congestive heart failure, etc. The reason for exclusion of any enrolled subject shall be documented on the screening log.
- Patient has known clinically-significant immune deficiency state (e.g., HIV infection).
- Patient is taking drugs with a low therapeutic index, such as warfarin, digoxin, and anti-seizure medications
- If patient has clinically suspected upper or lower gastrointestinal (GI) obstruction, they must be excluded or have been evaluated per standard of care and obstruction ruled out before screening. Determination of obstruction shall be documented on the screening log.
- History of fecal impaction with overflow diarrhea in the past 6 months
- History of Ileo-anal pouch
- History of allergy to silicone or one of its components
- Patient is pregnant and/or nursing
- Any other reason, which in the opinion of the Investigator, would confound proper interpretation of the study
- Patient whom, after training from a healthcare provider, cannot insert or expel the device themselves or with assistance from a caregiver
- History of anal or rectal pain and/or rectal bleeding in the past month
- Subject cannot retain either device (10 or 13 mm) while ambulating at the screening visit

- Post baseline anoscopy examination, presence of an anal fissure, Grade III-IV internal hemorrhoids, or thrombosed external hemorrhoids.

In addition, subjects will not be eligible to participate in the Treatment Period if during the baseline period or at the [REDACTED] visit:

- Used rescue medications beyond those allowed by the protocol

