6.3 MEASURES TO MINIMIZE BIAS: RANDOMIZATION AND BLINDING

This is a within-subject control study with a 4-week baseline period followed by a 2 to 4-week fitting period and a 4-week treatment period. Up to [REDACTED] subjects who meet all inclusion and meet no exclusion criteria at the end of the baseline phase of the study may be included in the optional [REDACTED] sub-study

Subjects who are candidates for screening into the study will be evaluated for eligibility by the Investigator to ensure that the inclusion and exclusion criteria have been satisfied. Once the subject signs the informed consent, they are considered enrolled in the study. At that time, the study site personnel will register the subject and assign a sequential and unique subject number. Once a subject number has been assigned, it cannot be reused.

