8 STATISTICAL CONSIDERATIONS

8.1 STATISTICAL HYPOTHESES

The hypotheses for the primary endpoints, which all apply to subjects with FI, are indicated below. For the primary study, these endpoints will be assessed for all 60 participants and separately for the 10 mm and 13 mm devices (versus baseline).

- 1. Primary Effectiveness Endpoint: A Relative Percentage Change in Episodes of Accidental Bowel Leakage (ABL) Determined by Comparing Treatment Results to Pre-treatment Results From the Baseline Period as Measured by Daily Diary Recordings . [Time Frame: Reduction in accidental bowel leakage from Baseline (Weeks 1-4) through Treatment period (approximately Weeks 9-12).]**

Measure Type	Primary
Measure Title	Primary Effectiveness Endpoint: A Relative Percentage Change in Episodes of Accidental Bowel Leakage (ABL) Determined by Comparing Treatment Results to Pre-treatment Results From the Baseline Period as Measured by Daily Diary Recordings.
Measure Description	This primary effectiveness endpoint will be calculated as a relative percentage of the baseline Accidental Bowel Leakage (ABL) using the following equation: % reduction in ABL = 100*(baseline period ABL - treatment period ABL) / (baseline period ABL)
Time Frame	Reduction in accidental bowel leakage from Baseline (Weeks 1-4) through Treatment period (approximately Weeks 9-12).

Secondary Efficacy Endpoint(s):

- The mean % reduction in Fecal Incontinence Severity Index (FISS) score from the baseline period to the end of the treatment period, calculated according to the following equation: % reduction in FISS = 100% (baseline period FISS - end treatment period FISS) / (baseline period FISS).
- The proportion of subjects in whom the frequency of FI episodes during the treatment period is greater than or equal to 75% lower than the frequency observed during baseline period.
- The proportion of subjects in whom, during treatment period, the device will reduce the number of days with FI by 50% as compared to baseline.
- The proportion of subjects in whom the device will reduce the volume of FI during the treatment period as compared to baseline.
- The proportion of subjects in whom the Minnesota Medical Technologies Anal Insert Device reduces the proportion of FI episodes which are associated with diarrhea.
- The proportion of subjects in whom the Minnesota Medical Technologies Anal Insert Device reduces the number of episodes of passive and of urge FI

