8.2 SAMPLE SIZE DETERMINATION

The sample size determination was based on literature review. In a controlled clinical trial with clonidine, the mean and standard deviation (SD) for weekly FI episodes over a 4 week baseline period was 2.642 and 1.066 respectively in the placebo group.²⁹

Assuming a mean frequency of 2.6 and a very conservative estimated SD of differences (post-pre treatment) of 1.3, a sample size of 13 subjects provides 90% power with a two sided paired t test and an alpha level of 0.05 to detect a 50% reduction (i.e., from 2.6 to 1.3 episodes/week) in the number of episodes of FI. Hence, a sample size of 30 FI subjects per group (i.e., 10mm and separately 13 mm inserts) is more than sufficient.

In order to test whether the treatment provides an improvement up to 60% response rate (50% response) from an assumed historical rate of 30%, the exact one-sample binomial test (2-sided) will be used at the 0.05 level. A sample size of n=30 provides 90% power to detect this effect.

No previous studies have evaluated [REDACTED]. We estimated that FI subjects [REDACTED] will [REDACTED] of the [REDACTED] (i.e., [REDACTED]). If [REDACTED] with a sample size of [REDACTED] in the [REDACTED] and [REDACTED] in the [REDACTED] (i.e., [REDACTED] devices), provides [REDACTED] [REDACTED].

For anoscopy, the sample size of 31 patients (i.e., 52%), provides 80% power to detect an event rate of 5% and 96% power to detect an event rate of 10%. In this context, an event refers to a side effect such as an anal fissure.

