8.3 POPULATIONS FOR ANALYSES

Male and female, aged 18 and above, with a diagnosis of fecal incontinence. For the main and the sub-study, the analyses will follow the intent to treat (ITT) paradigm with all subjects randomized included in the analyses. Subjects with missing values for a particular endpoint will have their missing values imputed using the corresponding overall mean value from all subjects with non-missing data for that endpoint. An adjustment in the ANCOVA error degrees of freedom (subtracting one for each imputed value) will be made to account for the imputation. A similar adjustment for the Wilcoxon rank sum test (adjusting the degrees of freedom for the t-approximation) will also be examined. Similar analyses will be performed for the completer cohorts, i.e., all subjects who completed the 4 week treatment bowel diary and the [REDACTED] sub-study. For the bowel diary study, the modified ITT (mITT) cohort, which comprises those subjects who entered treatment and completed at least 1 week of device use will also be considered.

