
from 4 week baseline period through 4 week treatment period (approximately 9-12 weeks).] 70% of subjects would have greater than or equal to 50% reduction in incontinence frequency.
 
2.
 
 ▪ Safety (AEs and SAEs) 	
 • The proportion of subjects in whom, during the treatment period, the device will reduce the number of days with FI by 50% as compared to baseline. • The proportion of subjects in whom the device will reduce the volume of FI during the treatment period as compared to baseline. • The proportion of subjects in whom the Minnesota Medical Technologies Anal Insert Device reduces the proportion of FI episodes which are associated with diarrhea. • The proportion of subjects in whom the Minnesota Medical Technologies Anal Insert Device reduces the number of episodes of passive and of urge FI • The proportion of subjects in whom the Minnesota Medical Technologies Anal Insert Device improves the Quality of Life (QOL) related to FI during the treatment period as compared to baseline. • The proportion of subjects in whom the Minnesota Medical Technologies Anal Insert Device will affect the composition of stool leakage during the treatment period as compared to baseline. • The proportion of subjects are satisfied with the Minnesota Medical Technologies Anal Insert Device. • The time for which a bowel movement can be deferred after the occurrence of urgency will be affected by the Minnesota Medical Technologies Anal Insert Device. • The proportion of complete bowel movements will be affected by the Minnesota Medical Technologies Anal Insert Device during the treatment period as compared to baseline. • Treatment with the Minnesota Medical Technologies Anal Insert Device will affect anxiety and depression during the treatment period as compared to baseline. • The Minnesota Medical Technologies Anal Insert Device reduces the use of medications for FI during the treatment period as compared to baseline. 	

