8.4.2 ANALYSIS OF THE PRIMARY AND SECONDARY EFFICACY ENDPOINT(S)

[REDACTED]
detailed methods for the analyses outlined below,

All bowel diary parameters (e.g., stool frequency, form, urgency, use of rescue medications, and FI) will be averaged first for each day and then over 4 weeks (baseline period and the last 4 of 12 weeks (approximately Weeks 9-12, treatment period) in each subject. These responses will also be assessed using ANCOVA models, with the corresponding baseline value as the primary covariate. [During the fitting period (approximately weeks 5-8), bowel diaries and questionnaires will be maintained to determine the right size of device. However, these data will not be used to evaluate the efficacy of the device.]

The analyses of the primary and secondary quantitative endpoints will utilize analysis of covariance (ANCOVA) models using corresponding baseline measurements, if available, as covariates. The adequate relief endpoint will first be summed over 4 treatment weeks, and then assessed using the Wilcoxon rank sum test. Treatment effects between groups (i.e., 10 mm vs 13 mm) will be evaluated, as appropriate with ANCOVA adjusted for the baseline variable. Individual adverse events (AEs) will be summarized and, where appropriate, (i.e., for parameters that are recorded during baseline and treatment bowel diaries such as pain during defecation), the overall frequency of AEs be compared using the Wilcoxon rank sum test. For the volume of FI episodes, a weighted score will be computed as follows (proportion of minor episodes*2 + proportion of major episodes*3).²⁵ An FI episode is defined as any episode of stool leakage that is more than a stain. A “minor FI episode” is more than a stain but not an entire bowel movement. A “major FI episode” is an entire bowel movement.

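### Section 8.4.2 names the rank sum test for AE frequency without saying what is compared; on the best reading (treatment versus each subject's own baseline) the data are paired and the signed-rank test is needed

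*Combined protocol and SAP*

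**What the plan says.** Section 8.4.2 says that individual AEs will be summarized and that, where appropriate, "the overall frequency of AEs be compared using the Wilcoxon rank sum test". It limits this comparison to a class of AEs: "for parameters that are recorded during baseline and treatment bowel diaries such as pain during defecation". The sentence does not name the two things being compared.

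Other parts of the plan bear on the contrast:

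- Section 6.3: "This is a within-subject control study with a 4-week baseline period".
- Section 8.1 assesses the endpoints against baseline, for all 60 participants and for each device size separately.
- Section 8.2 sizes the FI-episode comparison as a paired one: "a sample size of 13 subjects provides 90% power with a two sided paired t test".
- Section 8.3 mentions the test again ("A similar adjustment for the Wilcoxon rank sum test"), in connection with imputed values. No signed-rank test appears in the visible text.
- Section 8.4.4 gives only summary statistics for safety, so the sentence in 8.4.2 is the only formal AE test that can be seen.
- The outcome table in section 8.4.1 lists AEs and SAEs in the primary column, and section 7.3.3.3 lists new or increased anorectal pain as an anticipated risk.

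**The concern.** The comparison is limited to parameters that exist in both diaries. That limit makes most sense if the baseline diary is the comparator. Each subject then supplies both values, and the two sets of values are not independent samples.

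The rank sum test ignores the pairing. When a subject's baseline and treatment values are positively correlated, the true variability of the difference is smaller than the test assumes, so the test rejects too seldom. In an efficacy comparison that would be a cautious error. In a safety comparison it is not: a real increase in pain with the device becomes more likely to be reported as not significant.

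**Working it through.** **1. The plan's own paired calculation.** Section 8.2 assumes a mean of 2.6 weekly episodes, a reduction of 1.3 and an SD of differences of 1.3, with a two-sided paired t test at 0.05. From the noncentral t distribution with noncentrality (1.3/1.3)·√n, power is 88.3% at n = 12 and 91.1% at n = 13. The stated n = 13 for 90% power reproduces. This concerns FI episodes; the documents give no figure for the AE comparison.

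**2. Inputs for the AE comparison.** From the documents: 60 treated subjects (section 4.1) and 30 per size (section 8.2). The within-subject correlation ρ and the size of the shift are not given and are assumed. As a rough anchor, if FI episodes had SD 1.066 in both periods and SD of differences 1.3 (both figures from section 8.2), then ρ = 1 − 1.3²/(2 × 1.066²) = 0.26. Whether pain behaves alike is unknown.

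**3. True level of the rank sum test on paired data.** For normal data the level is approximately 2[1 − Φ(1.96/√(1 − ρₛ))], with ρₛ = (6/π)·arcsin(ρ/2). For ρ = 0, 0.3, 0.5 and 0.7 this gives 5.0%, 2.0%, 0.6% and 0.05%, against a nominal 5%.

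**4. Power by simulation, bivariate normal, two-sided 0.05, shift 0.35 SD.**

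| n | ρ | Rank sum: null level | Rank sum: power | Signed-rank: power |
|---|---|---|---|---|
| 60 | 0 | 4.9% | 46% | 46% |
| 60 | 0.3 | 1.9% | 45% | 59% |
| 60 | 0.5 | 0.8% | 43% | 73% |
| 60 | 0.7 | 0.1% | 45% | 92% |
| 30 | 0.3 | – | 21% | 33% |
| 30 | 0.5 | – | 18% | 45% |
| 30 | 0.7 | – | 13% | 65% |

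The signed-rank test stays near its 5% level throughout. At ρ = 0.26 with a shift of 0.4 SD and n = 60, power is 57% against 68%.

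**5. Diary-like counts.** Pain days out of 28 are taken as binomial with probability expit(μ + u), where u is normal with SD 1.5 and has correlation ρ between periods. The log-odds rise by 0.7 on treatment (odds about doubled), with n = 60 and ρ from 0.5 to 0.7.

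| μ | Pain-free at baseline | Rank sum power | Signed-rank power |
|---|---|---|---|
| −2.5 | 24% | 64–68% | 81–91% |
| −4 | 54% | 47–49% | 64–74% |
| −5.5 | 80% | 25–27% | 36–41% |

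At ρ = 0 the tests are about equal in all three rows. The gap narrows as baseline pain becomes rarer.

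**6. The limit of no baseline pain.** Suppose nobody has baseline pain and 5 of 60 develop it.

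- Exact rank sum: p = 2 × C(60,5)/C(120,5) = 0.057.
- Exact signed-rank: p = 2/2⁵ = 0.0625.
- Normal approximation: 0.023 for rank sum and 0.043 for signed-rank.

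Like for like, the signed-rank test gains nothing here.

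**The case against.** The strongest counter-argument is that 8.4.2 may mean 10 mm against 13 mm. Two sentences before the AE sentence, the adequate-relief endpoint is summed over the treatment weeks alone and assessed with the same test, which most naturally compares the device sizes. The next sentence names that contrast, although with ANCOVA, and section 8.4.5 speaks of comparing intervention groups. A requirement for both diaries would also fit a comparison of change from baseline between sizes. On that reading the groups are independent and the rank sum test is a legitimate choice. The supports for the paired reading in 8.1 and 8.2 concern efficacy; neither mentions AEs.

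This stands as a live alternative. It weakens the paired reading without displacing it: the limit to parameters in both diaries is in the AE sentence itself, and the study has no concurrent control. The size reading also needs a caveat. Under section 6.1.2, 10 mm starters with less than 75% reduction who are dissatisfied with comfort stay on 10 mm, and those dissatisfied on 13 mm return to it. The groups are thus non-randomised and partly chosen by comfort. A reader might infer that a by-size pain comparison must favour 13 mm. The documents do not support that: subjects who start directly on 13 mm stay on it whatever their comfort, and their number and proneness to pain are not stated.

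Two further objections hold. Redacted text opens 8.4.2 just before a mention of detailed methods, and it may state the contrast. Also, section 5.2 excludes "History of anal or rectal pain and/or rectal bleeding in the past month", which moves the trial towards the low-baseline end where the gain is small.

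Finally, no visible decision rule uses this p value, and sections 7.1 and 7.3.8 require anoscopy for new bleeding or for moderate or severe diary pain whatever the test shows. That limits the consequence; it does not make the test suit paired data.

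**Conclusion.** The point holds on the best reading of the sentence, with medium confidence. If AE frequency is compared between treatment and baseline in the same subjects, the rank sum test is invalid and, with positive correlation, conservative. With 60 subjects, an assumed shift of 0.35 SD and correlation 0.3 to 0.7, power is about 45% instead of 59% to 92%. The shift and the correlations are assumptions, not figures from the documents.

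A reader might take the 92% against 45% as the expected loss in this trial. The documents do not support that: it needs a correlation of 0.7 on normal data, the loss is nil at zero correlation, and it fades as baseline pain becomes rare. Nor do they show that the test is wrong on every reading, since between device sizes it would have independent groups.

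The effect is confined to a supporting safety comparison. The error costs power and does not create false positives when the correlation is positive. The primary effectiveness analysis is untouched. The sentence should still be corrected, because it is the only formal AE test in view and its likely failure is to miss a rise in pain.

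**What to change.** In section 8.4.2, replace the AE comparison with wording to this effect:

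*For AE parameters recorded in both the baseline and the treatment diary (for example, pain during defecation), each subject's treatment-period frequency is compared with that subject's own baseline frequency using the two-sided Wilcoxon signed-rank test. The number of subjects with new pain is reported beside the test. The rank sum test is used only for any comparison between device sizes, which is labelled non-randomised and exploratory.*

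If the redacted text already states a contrast, the visible sentence should be aligned with it, and the paired test used if that contrast is treatment against baseline.

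The cost is SAP wording only. Both diaries are already scheduled (section 1.3) and already record pain (section 7.1). The one drawback is that the signed-rank test has no power advantage if almost nobody has baseline pain, which is why the count of subjects with new pain belongs next to it.

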8.4.3 ANALYSIS OF THE SECONDARY ENDPOINT(S)

See section 9.4.2

8.4.4 SAFETY ANALYSES

Safety endpoints (e.g., adverse events, serious adverse events, unanticipated serious adverse events, device deficiencies, and device malfunctions) will be analyzed and reported with summary statistics. The start date, stop date, severity, relationship, expectedness, outcome, and duration of each AE will be reported. Adverse events leading to premature discontinuation from the study intervention and serious treatment-emergent AEs will be presented either in a table or a listing.

8.4.5 BASELINE DESCRIPTIVE STATISTICS

The intervention groups will be compared on baseline characteristics, including demographics and clinical features using descriptive statistics.

8.4.6 PLANNED INTERIM ANALYSES

There are no planned interim analysis for this study.

8.4.7 SUB-GROUP ANALYSES

Data for the primary endpoint will be evaluated separately in men and women, and also separately in younger and older subjects. The precise age cut off will depend on the distribution of subjects. Data for the secondary endpoints will be analyzed likewise.

8.4.8 TABULATION OF INDIVIDUAL SUBJECT DATA

If appropriate, individual subject data will be listed by measure and time point in the figures.

8.4.9 EXPLORATORY STUDY AND ANALYSES

STUDY

For the EXPLORATORY study, the [REDACTED], will be compared between both device groups (i.e, 10 and 13 mm) [REDACTED]. Similarly, [REDACTED] 10 and 13 mm devices will be compared [REDACTED]. The relationship between [REDACTED] will be compared [REDACTED]. Linear regression models will evaluate [REDACTED]. The [REDACTED] will be one or more of the following variables: [REDACTED]. The anal [REDACTED], proportion of subjects [REDACTED] and anorectal [REDACTED] [REDACTED] will be summarized.

ANALYSIS

[REDACTED] will be anonymized before being [REDACTED]. These results [REDACTED] will [REDACTED] Mayo Clinic or at other institutions.

The exploratory objectives are to:

- Evaluate the effects of the Minnesota Medical Technologies Anal Insert Device [REDACTED], as measured with [REDACTED]
- Evaluate if the effects of the Minnesota Medical Technologies Anal Insert Device [REDACTED] [REDACTED] the Minnesota Medical Technologies Anal Insert device [REDACTED]
- Evaluate the [REDACTED] subjects with FI

- Investigate [REDACTED] associated with FI [REDACTED]
[REDACTED] obtained at baseline

9 SUPPORTING DOCUMENTATION AND OPERATIONAL CONSIDERATIONS

9.1 REGULATORY, ETHICAL, AND STUDY OVERSIGHT CONSIDERATIONS

9.1.1 INFORMED CONSENT PROCESS

9.1.1.1 CONSENT/ASSENT AND OTHER INFORMATIONAL DOCUMENTS PROVIDED TO SUBJECTS

This study will be conducted in compliance with 21 CFR Parts 11, 50, 54, 56 and 812. The consent form is provided under separate cover.

9.1.1.2 CONSENT PROCEDURES AND DOCUMENTATION

Informed consent is a process that is initiated prior to the individual's voluntary documented agreement to participate in the study. Informed consent forms will be developed by the study sponsor together with the study site in a language and reading level understandable by the subject, reviewed by an accredited Institutional Review Board (IRB) and approved by the IRB prior to use. Each potential study subject will be asked to read and review the document. The investigator or designee will explain the research study to the subject and ensure enough time to answer any questions that may arise. The subjects should have the opportunity to discuss the study with their family or surrogates or think about it prior to agreeing to participate. The subject will sign and date the informed consent document prior to any procedures being done specifically for the study. Subjects must be informed that participation is voluntary and that they may withdraw from the study at any time, without prejudice, penalty, or loss of benefits. A copy of the informed consent document will be given to the subjects for their records. The informed consent process will be conducted and documented in the source document (including the date), and the form signed and dated, before the subject undergoes any study-specific procedures. The rights and welfare of the subjects will be protected by emphasizing to them that the quality of their medical care will not be adversely affected if they decline to participate in this study.

